#### **9.1.3.2. Real-world PFS**

Real-world PFS is defined as the following:

- Real-world PFS, defined as time from start of avelumab/axitinib treatment to date of first disease progression (as clinically assessed by local investigator based on radiology, laboratory evidence, pathology, or other assessments) or death due to any cause, whichever came first  
If there were no clinical records of death or disease progression, they were censored at the date of initiation of the next line of therapy for the patients undertaking two or more lines of therapy based on the record, or at their last visit date during the study period for the patients undertaking only one line of therapy based on the record.

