## **9.7. Data analysis**

Detailed methodology for summary and statistical analyses of data collected in this study will be documented in a statistical analysis plan (SAP), which will be dated, filed, and maintained by the sponsor. The SAP may modify the plans outlined in the protocol; any major modifications of primary endpoint definitions or their analyses would be reflected in a protocol amendment.

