6.3 Derivation variables

1) Survival time analysis

It is defined as follows:

Endpoint	Start date	End date (event)	End date (censor)
Real-world PFS	Date treatment with avelumab and/or axitinib was initiated (if not on the same day, whichever occurs earlier)	Date of first disease progression (clinical evaluation based on radiological, laboratory, pathological, or other evaluation by the principal investigator) or death from any cause, whichever occurs earlier	Date of last confirmation of progression-free survival or start of subsequent treatment (whichever occurs earlier)
TTF of avelumab and axitinib	Date treatment with avelumab and/or axitinib was initiated	Date of completion of treatment with avelumab and/or axitinib	Date of last confirmation of progression-free survival or date of last dose in case of efficacy stopping (whichever date occurs earlier)
TTF of avelumab	Date treatment with avelumab was initiated	Date of completion of treatment with avelumab	Date of last confirmation of progression-free survival or date of last dose in case of efficacy stopping (whichever date occurs earlier)
TTF of axitinib	Date treatment with axitinib was initiated	Date of completion of treatment with axitinib	Date of last confirmation of progression-free survival or date of last dose in case of efficacy stopping (whichever date occurs earlier)

2) Objective response rate

ORR is defined as the proportion of patients with a CR or PR as the best overall response in tumor assessment during the observation period, as assessed by an investigator under actual clinical practice, including assessment based on RECIST ver. 1.1.

3) Calculation of duration

Duration	Definition
Duration of avelumab treatment	Date of last dose – date of initial dose + 14
Duration of axitinib treatment	Date of last dose – date of initial dose + 1
Duration of non-administration	Date of end – Date of start + 1

4) Corticosteroid equivalent dose (prednisolone equivalent)

This will be calculated as shown in the table below.

Generic name	Corresponding amount (mg)	Prednisolone conversion ratio
Cortisone	25	0.2
Hydrocortisone	20	0.25
Prednisolone	5	1
Methylprednisolone	4	1.25
Triamcinolone	4	1.25
Dexamethasone	0.75	6.7
Betamethasone	0.6	8.3

5) Date of initial dose

If avelumab and axitinib are administered for different durations, the earlier of the two dates should be used as the date of the initial dose.

6) Date of last confirmation of progression-free survival

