If there is no or unknown data of progressive disease (PD) in the [Progressive disease (PD) information] of the CRF, the date of diagnosis shall be the date of confirmation of the last progression-free survival.

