9 CHANGES FROM THE PROTOCOL

Not applicable.

Last page

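### Protocol and SAP censor real-world PFS at different dates, the SAP date is not properly defined, and SAP section 9 declares no change from the protocol

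*Protocol*

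**What the plan says.** Protocol 9.1.3.2 gives two censoring dates for patients with no record of progression or death. Those who went on to further treatment are "censored at the date of initiation of the next line of therapy for the patients undertaking two or more lines of therapy". The rest are censored "at their last visit date during the study period for the patients undertaking only one line of therapy".

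The survival-time table in SAP 6.3 gives one rule for everyone: "Date of last confirmation of progression-free survival or start of subsequent treatment (whichever occurs earlier"). Item 6 of the same section covers patients whose CRF shows progression as absent or unknown: "the date of diagnosis shall be the date of confirmation of the last progression-free survival". It does not say which diagnosis, name a CRF field, or mention the last visit.

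Under "9 CHANGES FROM THE PROTOCOL" the SAP's entire entry is "Not applicable".

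Protocol 9.7 states that "The SAP may modify the plans outlined in the protocol", and asks for a protocol amendment only for major changes to primary endpoints. Real-world PFS is a secondary endpoint (Protocol 9.1.2).

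**The concern.** A clinic visit and a confirmation that the patient is progression-free are different records and can carry different dates. A reader of the protocol expects last-visit censoring. A programmer working from the SAP table would use another date and, finding item 6 unclear, might fall back on the protocol. Nothing tells either of them that the rules differ.

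The choice reaches reported results. SAP 8.3.1.2 applies the TTF analysis of 8.3.1.1 to PFS: Kaplan-Meier estimates every 3 months, the median, and events per 100 person-years. Follow-up is short, so under a plausible median more than half the patients would be censored and open to the rule. If the rule is settled only after the data are seen, the PFS summary becomes partly a matter of choice.

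**Working it through.** The plan gives no expected PFS, event count or power for this study, so there is no figure to reproduce.

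**Step 1: the rules side by side**

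| Patient without recorded event | Protocol 9.1.3.2 | SAP 6.3 |
|---|---|---|
| One line of therapy | Last visit | Last progression-free confirmation |
| Two or more lines | Start of next line | Earlier of last progression-free confirmation and start of next line |

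If the last confirmation falls on or before the last visit, the SAP date is never later than the protocol date. On the same events, person-time is then equal or smaller, incidence equal or higher, and the Kaplan-Meier curve equal or lower.

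**Step 2: inputs**

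- Follow-up: 6 to 18 months (index dates 20 December 2019 to 20 December 2020, cut-off 20 June 2021; Protocol 9.1). Uniform entry is assumed.
- Median PFS: 13.8 months, from the phase 3 trial cited in Protocol 7. Using it here, with an exponential shape, is an assumption.
- Patients: about 70 (Protocol 9.5).
- Last visit at cut-off: assumption.
- Gap between last confirmation and last visit: not in the documents. It is varied as if assessments came every s = 2, 3 or 4 months, giving a mean gap of about s/2.

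**Step 3: incidence by arithmetic, progression recorded when it occurs**

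- λ = ln 2 / 13.8 = 0.0502 per month.
- Proportion censored = (e^(−6λ) − e^(−18λ)) / (12λ) = (0.740 − 0.405) / 0.603 = 0.556. Proportion with an event = 0.444, or about 31 of 70.
- Mean person-time, protocol rule = 0.444 / 0.0502 = 8.85 months. Incidence = 1200 × λ = 60.3 per 100 person-years.
- Mean person-time, SAP rule = 8.85 − 0.556 × s/2:
  - s = 2: 8.29 months, incidence 64.3 (+7%)
  - s = 3: 8.01 months, incidence 66.5 (+10%)
  - s = 4: 7.74 months, incidence 68.9 (+14%)

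**Step 4: the curve, same detection model**

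A simulation of 40,000 patients, with the gap uniform from 0 to s months, gives:

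| Rule | Events per 100 person-years | Median (months) | 12-month PFS |
|---|---|---|---|
| Protocol (gap 0) | 60.6 | 13.7 | 54.5% |
| SAP, s = 2 | 64.6 | 12.7 | 52.3% |
| SAP, s = 3 | 66.9 | 12.3 | 51.0% |
| SAP, s = 4 | 69.2 | 11.9 | 49.5% |

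The 12-month estimate falls by 2.2, 3.5 and 5.0 points.

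**Step 5: progression found only at assessments**

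Simulated 3-monthly assessments give 50.7 (protocol) against 56.0 (SAP) events per 100 person-years. For 2-, 3- and 4-monthly assessments the SAP rate is 7%, 10% and 15% higher. At 3 months, 12-month PFS is 54.7% under both rules, because no event can fall between the last assessment and the last visit.

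**Step 6: sampling error**

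- With 31 events, the exact Poisson 95% limits are about 21.1 and 44.0, or 32% below to 42% above the estimate.
- For 12-month PFS, √(0.547 × 0.453 / 70) = 0.059 before allowing for censoring. With censoring the standard error is about 7 points, an interval of roughly ±13 points.

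**The case against.** **The SAP may differ from the protocol.** Protocol 9.7 allows it, and PFS is secondary, so no amendment was compulsory. The SAP is also the detailed analysis document. This stands, and it rules out reading the mismatch as a breach. It does not make the entry in SAP section 9 correct: a permitted change still has to be declared.

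**The shifts are small for a descriptive study of about 70 patients.** This also stands, and no decision rule hangs on PFS. But both rules act on the same patients, so the difference between them is systematic rather than noise, and no confidence interval will display it.

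Four stronger readings are tempting, and the documents do not support them:

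- *Last-visit censoring is the biased rule, because it credits time in which progression could not be seen.* Protocol 9.1.3.2 accepts laboratory, pathological or other evidence as well as radiology, and counts death. Events can therefore arise between scans. If progression is recorded when it occurs, the protocol rule is close to the assumed truth (60.6 against 60.3 per 100 person-years) and the SAP rule overstates the rate. If it is found only at assessments, 12-month PFS is the same under both.
- *The dates differ for nearly every censored patient.* No scan or visit schedule is given. Where the last visit is also the last assessment, the rules agree.
- *Item 6 means the mRCC diagnosis, giving negative times.* The wording permits this, since that diagnosis precedes treatment, but item 6 refers to the progression page of the CRF and may mean an assessment date. The text shows ambiguity, not that this date would be programmed.
- *The number of events also differs.* The SAP does not say how it handles progression or death after subsequent treatment starts, so this cannot be decided. The figures above take the events as the same.

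**Conclusion.** The point holds as an unreconciled definition. Two censoring rules are in force for real-world PFS, the date that drives the SAP's rule is undefined, and SAP section 9 is wrong to declare no change.

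The direction is clear provided the last progression-free confirmation is never later than the last visit: the SAP rule then gives an equal or higher event rate. The size rests on a gap that the documents do not supply. Under the assumptions in the working, incidence is about 7% to 15% higher under the SAP rule. Twelve-month PFS is either unchanged or about 2 to 5 points lower, depending on how progression comes to be recorded. With a zero gap there is no difference.

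These shifts are within the study's sampling error, and nothing here shows which rule is the less biased. The matter should be settled because it changes reported results and is cheap to settle in advance.

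**What to change.** Before data lock (Protocol 9.7.4 requires the SAP to be fixed by then):

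1. Choose one censoring rule for real-world PFS. State it identically in Protocol 9.1.3.2 and SAP 6.3, or keep the SAP rule and list the change in SAP section 9.
2. Replace the date of diagnosis in SAP 6.3 item 6 with a named CRF date on or after treatment start, for example the last assessment documented as without progression. The three TTF endpoints use the same date for censoring, so one definition serves all.
3. Report the rule not chosen as a sensitivity analysis for the Kaplan-Meier estimates and the incidence rate.

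The cost is wording and one extra analysis. It needs no additional patients, and no additional data if the CRF already holds both dates.

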#### **9.1.3.3. Objective response (OR)**

OR is defined as the following:

- Complete or partial response as the best adjudication result (complete response [CR] > partial response [PR] > stable disease [SD] > progressive disease [PD], unknown) in a method complies with RECIST version 1.1 tumor assessment as closely as possible in clinical practice by investigator's judgment.

## **9.2. Setting**

This study is a post-approval, company-sponsored, observational study.

### **9.2.1. Inclusion criteria**

Patients must meet all of the following inclusion criteria to be eligible for inclusion in the study:

- 1) Diagnosed with mRCC based on the General Rule for Clinical and Pathological Studies on Renal Cell Carcinoma (4th Edition) before receiving avelumab plus axitinib as a first-line therapy;
- 2) Over 20 years of age at the time of mRCC diagnosis;
- 3) Start treatment with avelumab plus axitinib as a first-line therapy for mRCC from 20 December 2019 to 20 December 2020;
- 4) For patients who are still alive and have routine visits to the study site, evidence of a personally signed and dated informed consent document indicating that the patient has been informed of all pertinent aspects of the study. For patients who are still alive and had been transferred to another hospital, evidence that the patient has been informed of all pertinent aspects of the study and oral or written informed consent is obtained.
- 5) Deceased patients are also included for inclusion criteria 1-3.

#### **9.2.2. Exclusion criteria**

There are no exclusion criteria for this study.

#### **9.3. Variables**

The following information will be collected in this study. Human genome and gene information will not be collected.

##### **9.3.1. Patient characteristics at baseline**

- The following data regarding the patients characteristics will be collected at baseline: age, sex, BMI, ECOG PS, IMDC risk score, pathological diagnosis: Fuhrman grade, histological type, Sarcoid component, Number of metastatic organs and site of metastases, TNM classification, complications, nephrectomy, renal function: eGFR, proteinuria, CRP level, smoking history, and concomitant use of drugs. Patient characteristics to be collected at baseline include the most recent data prior to initial treatment with avelumab plus axitinib.

##### **9.3.2. IMDC risk -related data at baseline**

The following IMDC risk-related data will be collected:

- 1) <1 year from time of diagnosis to systemic therapy;
- 2) Karnofsky Performance Status <80%;
- 3) Hemoglobin < lower limit of normal;
- 4) Corrected calcium > upper limit of normal;
- 5) Neutrophils > upper limit of normal;
- 6) Platelets > upper limit of normal.

### **9.3.3. Clinical outcome (Real-world PFS)**

Definitions of Real-world PFS is defined in [Section 9.1.3](#). The following data will be collected to determine the clinical outcomes: date of start of treatment, date of first disease progression or death due to any cause, whichever came first.

### **9.3.4. Clinical outcome (OR)**

Definitions of OR is defined in [Section 9.1.3](#). The following data will be collected to determine the clinical outcomes: tumor assessment (CR, PR, SD, PD, and unknown)

### **9.3.5. Avelumab treatment (TTF)**

Definitions of TTF is defined in [Section 9.1.3](#). The following avelumab treatment data will be collected: date of administration, actual and standard dosage, and reason for discontinuation and interruption.

### **9.3.6. Axitinib treatment (TTF)**

Definitions of TTF is defined in [Section 9.1.3](#). The following axitinib treatment will be collected: date of administration, reason for dose increase, dose reduction, actual and standard dosage, and reason for discontinuation and interruption.

### **9.3.7. Corticosteroid treatment**

The following corticosteroid treatment data for irAE will be collected: date of treatment, drugs of corticosteroid, dose of corticosteroid, cumulative dose of corticosteroid, duration of treatment, and number of administrations during the treatment with avelumab plus axitinib.

### **9.3.8. Pre-medication and treatment for infusion-related reaction of avelumab**

The following pre-medication and treatment data will be collected: Presence of pre-medication, therapeutic drugs for infusion-related reaction of avelumab and presence of treatment for infusion-related reaction of avelumab.

### **9.3.9. Second-line regimen after avelumab plus axitinib treatment**

The following second-line regimen data will be collected: medication after avelumab plus axitinib treatment.

## **9.4. Data sources**

As this is a retrospective study, all data will be collected from medical records at the participating study site.

## **9.5. Study size**

This study is descriptive study which aims to describe the demographic and baseline characteristics of patients who were treated avelumab plus axitinib in first-line treatment for mRCC, rather than testing any pre-defined hypothesis. Since all the analyses will be descriptive, sample size calculations are not applicable.

The expected number of patients will be approximately 70 patients in total, but the number should be considered flexible.

## **9.6. Data management**

Investigators will fill out electronic case report forms (eCRFs) based on the medical charts by electronic data capture (EDC). After the completion, eCRFs are transferred to a single electronic database. Only the de-identified and anonymized data are included.

When receiving a query from the sponsor on the completed eCRF (ie, Data Clarification Form [DCF]), investigators will reconfirm the information on source documents, fill out the DCF as required, and submit the DCF.

### **9.6.1. Electronic Case report forms (eCRFs)/Data collection tools (DCTs)/Electronic data record**

As used in this protocol, the term CRF should be understood to refer to either a paper form or an electronic data record or both, depending on the data collection method used in this study.

An eCRF is required and should be completed for each included patient. The completed original eCRFs are the sole property of Pfizer and should not be made available in any form to third parties, except for authorized representatives of Pfizer or appropriate regulatory authorities, without written permission from Pfizer. The investigator shall ensure that the eCRFs are securely stored at the study site in encrypted electronic form and will be password protected to prevent access by unauthorized third parties.

The investigator has ultimate responsibility for the collection and reporting of all clinical, safety, and laboratory data entered on the eCRFs and any other data collection forms (source documents) and ensuring that they are accurate, authentic/original, attributable, complete, consistent, legible, timely (contemporaneous), enduring, and available when required. The eCRFs must be signed by the investigator or by an authorized staff member to attest that the data contained on the eCRFs are true. Any corrections to entries made in the eCRFs or source documents must be dated, initialed, and explained (if necessary) and should not obscure the original entry.

The source documents are the hospital or the physician's chart. In these cases, data collected on the eCRFs must match those charts.

### **9.6.2. Record retention**

To enable evaluations and/or inspections/audits from regulatory authorities or Pfizer, the investigator agrees to keep records, including the identity of all participating patients (sufficient information to link records, eg, eCRFs and hospital records), all original signed informed consent documents, copies of all eCRFs, safety reporting forms, source documents, detailed records of treatment disposition, and adequate documentation of relevant correspondence (eg, letters, meeting minutes, and telephone call reports). The records should be retained by the investigator according to local regulations or as specified in the clinical

study agreement (CSA), whichever is longer. The investigator must ensure that the records continue to be stored securely for so long as they are retained.

If the investigator becomes unable for any reason to continue to retain study records for the required period (eg, retirement, relocation), Pfizer should be prospectively notified. The study records must be transferred to a designee acceptable to Pfizer, such as another investigator, another institution, or to an independent third party arranged by Pfizer.

Study records must be kept for a minimum of 15 years after completion or discontinuation of the study, unless Pfizer have expressly agreed to a different period of retention via a separate written agreement. Record must be retained for longer than 15 years if required by applicable local regulations.

The investigator must obtain Pfizer's written permission before disposing of any records, even if retention requirements have been met.

### **9.6.3. Record disposal**

Study records must be disposed of appropriately according to each site regulation.

## **9.7. Data analysis**

Detailed methodology for summary and statistical analyses of data collected in this study will be documented in a statistical analysis plan (SAP), which will be dated, filed, and maintained by the sponsor. The SAP may modify the plans outlined in the protocol; any major modifications of primary endpoint definitions or their analyses would be reflected in a protocol amendment.

### **9.7.1. Analysis Population**

Will be provided in the SAP.

### **9.7.2. Analysis Methods**

Continuous variables will be summarized using descriptive statistics ie, number of non-missing values and number of missing values [ie, n (missing)], mean, median, standard deviation (SD), minimum, maximum and first and third quartile.

Qualitative variables will be summarized by frequency counts and percentages.

For the time-to-event endpoints, eg, TTF and Real-world PFS, the Kaplan-Meier estimates (product-limit estimates) will be presented together with a summary of associated statistics including the median Real-world PFS time with 2-sided 95% CIs. In particular, the Real-world PFS rate at several timepoints will be estimated with corresponding 2-sided 95% CIs. These endpoint will also be displayed graphically.

### **9.7.3. Analysis of Primary Endpoints**

See [Section 9.1.3](#). These endpoints will also be displayed graphically if necessary.

#### **9.7.4. Analysis of Secondary Endpoints**

##### **Efficacy Endpoints**

See [Section 9.1.3](#). These endpoints will also be displayed graphically if necessary.

##### **Other Secondary Endpoints**

See [Section 9.1.3](#). These endpoints will also be displayed graphically if necessary.

The SAP must be fixed before data lock. The final analysis will be performed after data lock and may modify the plans outlined in the protocol.

#### **9.8. Quality control**

The sponsor will train investigators and study site staff with an onsite training visit or web-training on the protocol, eCRFs, and any applicable study processes. Any new information relevant to the performance of this study will be forwarded to the investigator and study site staff during the study. Remote data monitoring will be conducted during the life of the study to ensure timely reporting of data, data integrity, and consistency. eCRFs for all included patients will be made available to the remote data monitor for review. The study sites will be queried and managed to request resolution to any issues that may arise during the course of the study.

